5. BMI
6. Surgical approach
7. ASA physical status
8. Average amount of opioids consumed daily in the week prior to surgery
9. VAS scores immediately postoperatively in the recovery room, 24 hours postoperatively
10. Opioid consumption intraoperatively and postoperatively
11. Physical therapy assessments
 1. Degree of independence in mobility and transfers at 24 hours
 2. Ambulation distance at 24 hours
12. Time to discharge from the hospital

Projected Overall Study Timeline

Date	Study Start-Up	Enrollment	Data Entry and Analysis	Study Write-Up
12 2020	X			
01 2021		X		
04 2021			X	
05 2021				X

7.0 PLAN FOR STUDY: [Click here to enter text.](#)

- a. What is the potential impact of your study findings (e.g., how will findings impact clinical outcomes)? This study will compare the quality of recovery after total hip arthroplasty with PENG block for postoperative pain control versus no PENG block. The PENG block targets only the sensory branches and not the posterior mechanoreceptors; there is a potential motor-sparing effect which is desirable for early ambulation, better physical therapy, and earlier discharge. The effective analgesia and early ambulation provided by such regional anesthesia block may have positive impact on patient's mood, sleep, appetite and overall feeling of well-being. It remains unclear whether PENG block

provides sufficient analgesia and improves the quality of post-operative recovery after primary THA. .

- b. Do you plan to submit an abstract based on this project? Yes No (If yes, to which meeting venue? American Society of Regional Anesthesia
- c. Do you intend to publish the finding from this research project: Yes No

8.0 DRUG INFORMATION (if applicable)

Drug Name: 0.75% Bupivacaine

Other Names: Marcaine

Classification: Amino-amide local anesthetic

Mode of Action: Blocks both the initiation and conduction of nerve impulses by decreasing the neuronal membrane's permeability to sodium ions, which results in inhibition of depolarization with resultant blockade of conduction

Storage and Stability: store at 20-22 degree centigrade (Room Temperature)

Metabolism: Hepatic metabolism via CYP1A2 (minor), CYP2C19 (minor), CYP2D6 (minor), CYP3A4 (minor). Local anesthetics and their metabolites are excreted by the kidney. Urinary excretion is affected by urinary perfusion and factors affecting urinary pH. Only 6% of bupivacaine is excreted unchanged in the urine.

Preparation: Bupivacaine Hydrochloride is a sterile isotonic solution containing 2.5 mg/ml bupivacaine, 5 mcg/ml epinephrine and 8.5 mg/ml sodium chloride

Administration: Local infiltration, peripheral nerve block, retrobulbar block, sympathetic block, lumbar epidural, caudal

Incompatibilities: Bupivacaine with epinephrine should not be used concomitantly with ergot-type oxytocic drugs, because a severe persistent hypertension may occur. Likewise, solutions of bupivacaine hydrochloride containing a vasopressor such as epinephrine should be used with extreme caution in patients receiving monoamineoxidase inhibitors (MAOI) or antidepressants of the triptyline or imipramine types, because severe prolonged hypertension may result.

- **Contraindications:** Hypersensitivity to bupivacaine, amide-type local anesthetics, or any component of the formulation; obstetrical paracervical block anesthesia. Until further experience is gained in pediatric patients younger than 12 years, administration of bupivacaine in this age group is not recommended. There have been reports of cardiac arrest and death during the use of bupivacaine hydrochloride for intravenous regional anesthesia (Bier block). Information on safe dosages and techniques of administration of bupivacaine hydrochloride in this procedure is lacking. Therefore, bupivacaine hydrochloride is not recommended for use in this technique.
- **Precautions:** The lowest dosage of local anesthetic that results in effective anesthesia should be used to avoid high plasma levels and serious adverse effects. The rapid

injection of a large volume of local anesthetic solution should be avoided and fractional [incremental] doses should be used when feasible. Local anesthetic solutions containing a vasoconstrictor should be used cautiously and in carefully restricted quantities in areas of the body supplied by end arteries or having otherwise compromised blood supply such as digits, nose, external, ear, or penis. Patients with hypertensive vascular disease may exhibit exaggerated vasoconstrictor response. Ischemic injury or necrosis may result. Because amide-local anesthetics are metabolized by the liver, these drugs, especially repeat doses, should be used cautiously in patients with hepatic disease. Patients with severe hepatic disease, because of their inability to metabolize local anesthetics normally, are at a greater risk of developing toxic plasma concentrations. Local anesthetics should also be used with caution in patients with impaired cardiovascular function because they may be less able to compensate for functional changes associated with the prolongation of AV conduction produced by these drugs.

Click here to enter text.

Side Effects: Adverse effects indicated in *italics* are the most frequent adverse effects. Adverse events in **bold** are severe/life-threatening, otherwise they are mild to moderate in reaction.

CNS: ***Seizures:** convulsions due to systemic toxicity leading to cardiac arrest have also been reported, presumably following unintentional intravascular injection or administration near the head or neck.*

CV: *arrhythmias, cardiac arrest, death*

EENT: ***Respiratory arrest**, especially when administered near the head or neck*

ENDO: Click here to enter text.

GI: Click here to enter text.

GU: Click here to enter text.

INTEG: Click here to enter text.

MS: *Intra-articular infusion related chondrolysis: Continuous intra-articular infusion of local anesthetics after arthroscopic or other surgical procedures is not an approved use; chondrolysis (primarily shoulder joint) has occurred following infusion, with some patients requiring arthroplasty or shoulder replacement.*

Investigational New Drug (IND) Application required (check yes or no): Yes No

Will the research Pharmacy be involved in the ordering, storage, dispensing and blind of the study drug? Yes No

8.0 DRUG INFORMATION (if applicable)

Drug Name: 2% Lidocaine

Other Names: Click here to enter text.

Classification:	Amide-type local anesthetic
Mode of Action:	Cardiac antiarrhythmic effect is exerted by increasing the electrical stimulation threshold of the ventricle during diastole
Storage and Stability:	Room temperature (25°C); brief exposure up to 40°C does not adversely affect the product
Metabolism:	90% hepatic metabolism; 10% renally excreted, unchanged
Preparation:	Lidocaine hydrochloride and 5% dextrose injection is a sterile, nonpyrogenic solution prepared from lidocaine hydrochloride and dextrose in water for injection.
Administration:	Intravenous, local infiltration
Incompatibilities:	Lidocaine should be used with caution in patients with digitalis toxicity accompanied by atrioventricular block. Coadministration of propranolol or cimetidine with lidocaine has been reported to reduce the clearance of lidocaine from the plasma and may result in toxic accumulation of the drug. When lidocaine is administered with other antiarrhythmic drugs such as amiodarone, phenytoin, procainamide, propranolol or quinidine, the cardiac effects may be additive or antagonistic and toxic effects may be additive. Phenytoin may stimulate the hepatic metabolism of lidocaine, but the clinical significance of this effect is not known.

- *Contraindications: Lidocaine hydrochloride is contraindicated in patients with a known history of hypersensitivity to local anesthetics of the amide type. Lidocaine should not be used in patients with Stokes-Adams syndrome, Wolff-Parkinson-White syndrome, or with severe degrees of sinoatrial, atrioventricular or intraventricular block. Solutions containing dextrose may be contraindicated in patients with known allergy to corn or corn products.*
- *Precautions: Caution should be employed in the repeated use of lidocaine hydrochloride in patients with severe liver or renal disease because accumulation may occur and lead to toxic phenomena, since lidocaine hydrochloride is metabolized mainly in the liver and excreted by the kidneys. The drug should also be used with caution in patients with hypovolemia and shock and in all forms of heart block. In patients with sinus bradycardia or incomplete heart block, the administration lidocaine hydrochloride intravenously for the elimination of ventricular ectopic beats without prior acceleration in heart rate (by isoproterenol or electric pacing) may promote more frequent and serious ventricular arrhythmias or complete heart block. Most potent anesthetic agents, local anesthetics of the amide type, which includes lidocaine, and muscle relaxants of both depolarizing and non-depolarizing types, have been associated with malignant hyperthermia.*

Click here to enter text.

Side Effects: Adverse effects indicated in *italics* are the most frequent adverse effects. Adverse events in **bold** are severe/life-threatening, otherwise they are mild to moderate in reaction.

CNS: respiratory depression and arrest; unconsciousness; convulsions; tremors; twitching; vomiting; blurred or double vision; drowsiness; dizziness; light-headedness; tinnitus; sensation of heat, cold or numbness; euphoria, apprehension

CV: Prolongation of PR interval, widening of the QRS interval and appearance or aggravation of arrhythmias

EENT: Click here to enter text.

ENDO: **Methemoglobinemia**

GI: Click here to enter text.

GU: Click here to enter text.

INTEG: Click here to enter text.

MS: Click here to enter text.

Investigational New Drug (IND) Application required (check yes or no): Yes No

Will the research Pharmacy be involved in the ordering, storage, dispensing and blind of the study drug? Yes No

DEVICE INFORMATION (if applicable)

Device Name: Click here to enter text. **Other Names:** Click here to enter text.

Classification: Click here to enter text.

Mechanism of Action: Click here to enter text.

Medication(s) Delivered: Click here to enter text.

Incompatibilities: Click here to enter text.

Contraindications: Click here to enter text.

Precautions: Click here to enter text.

SIDE EFFECTS: Adverse effects indicated in *italics* are the most frequent adverse effects. Adverse events in **bold** are severe/life-threatening, otherwise they are mild to moderate in reaction.

CNS: Click here to enter text.

CV: Click here to enter text.

EENT: Click here to enter text.

ENDO: Click here to enter text.

GI: [Click here to enter text.](#)

GU: [Click here to enter text.](#)

INTEG: [Click here to enter text.](#)

MS: [Click here to enter text.](#)

Investigational Device Exemption (IDE) required check yes or no: Yes No (If yes, provide details. [Click here to enter text.](#))

9.0 STATISTICAL CONSIDERATIONS

General Data Analysis Plan:

The distribution of the continuous factors will be examined using data visualization techniques such as q-q plots and the Shapiro-Wilk test. All normally distributed demographic and continuous variables will be expressed as means and standard deviations; categorical factors will be expressed as proportions. For non-normal data, the medians and inter quartile ranges will be displayed. For data that are normally distributed, Student's t-test will be used to compare the groups. For data that are not normally distributed, a Mann-Whitney tests will be used for comparisons. Chi-square or Fisher's exact tests will be used to analyze categorical data. Time to event data such as distance of first ambulation will be analyzed using Kaplan-Meier curves. The planned sub-group analysis will be conducted for GA vs. Spinal using a 2x2 ANOVA test. For all comparisons, a value of $p < 0.05$ will be considered statistically significant. Statistical analyses will be performed using SAS for Windows, version 9.2.

Statistical Power and Sample Size Estimates: Fifty-six patients in each group are required to detect a Minimal Clinically Important Difference (MCID) of 8 points for QoR-15 score assuming a standard deviation of 15 points using data from previous studies (19, 20) for 5% significance level and 80% power.

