2.0 Background and Rationale

As the practice of anesthesiology has grown increasingly safe, the focus has shifted to improving quality, as evidenced by the robust spread of Enhanced Recovery after Surgery protocols. The implications from poor quality recovery is vast, including prolonged stay in the recovery room or hospital [7]. The Quality of Recovery (QoR-15) questionnaire is a method to measure five dimensions using 15 questions: physical independence, pain, comfort, patient support, emotional state [8]. It is an extensively validated measure of patient-assessed quality of recovery after surgery, having been demonstrated over a variety of clinical settings. QoR-15 scores range from 0 (extremely poor quality of recovery) to 150 (excellent). Mean time to complete the 15-question survey is 3 minutes, a marker of its clinical utility [9]. As we aim to improve our perioperative care and develop approaches to improve medicine in this regard, the QoR-15 provides a useful tool.

The effective postoperative analgesia is vital as acute surgical pain is a potential risk factor for future chronic pain. Persistent pain after THA (more than three months) is reported in 27% of patients and is reported to be correlated with the intensity of early postoperative pain

rather than preoperative pain levels [10,11]. Utilizing regional anesthesia helps to limit the use of opioids, however, which technique is best has yet to be determined. The lumbar plexus blocks, lumbar epidurals, and femoral nerve blocks have been associated with motor weakness. Fascia iliaca compartment block (FICB) has not been found to predictably decrease pain intensity or opioid use [12]. Quadratus lumborum (QL) block is a relatively new regional block found to provide effective analgesia after primary THA, but it can indirectly block lumbar plexus branches and may cause some motor weakness [13]. It is also a deep block and therefore contraindicated in patients on anticoagulation [14].

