 - After the PENG block is placed, patients will have THA under spinal or general anesthesia. Spinal anesthesia will be provided by intrathecal injection of hyperbaric (0.75%) bupivacaine. General anesthesia will be provided by propofol induction, rocuronium for muscle relaxation and inhalation anesthetics for maintenance. Patients will receive fentanyl 25-50 mcg iv for increase in systolic blood pressure (SBP) > 25% of baseline SBP. Intraoperatively patients will also receive 4mg dexamethasone iv and 4 mg ondansetron iv.
 - Control group participants will be transferred to the block area preoperatively, and care will proceed as if they were receiving injection.
 - Patients will be placed in the supine position resting comfortably. Standard noninvasive monitors will be applied, and oxygen will be administered via nasal cannula. Parenteral midazolam and fentanyl will be titrated to patient comfort. Standard skin sterilization, prepping and draping will be applied to the area. The ultrasound probe will be used to

identify the iliopubic eminence (IPE). Only skin will be numbed using 2-3 cc of 2% lidocaine and NO bolus of bupivacaine will be injected.

- Postoperative patients in both the PENG arm and the control arm will be given scheduled PO acetaminophen 975 mg BID, and celecoxib 200mg BID (Dose of celecoxib will be adjusted based on renal function, and no celecoxib will be given for GFR < 30 ml/min) as part of multimodal pain regimen. Patients will be given a standard pain regimen of PRN Oxycodone 5 mg Q 4 hours for breakthrough pain, and hydromorphone 1mg IV every 6 hours prn as rescue analgesia for severe pain (NRS score more than 7/10). Patients will get prn ondansetron 4 mg iv every 4 hours. Naloxone iv prn will be used for any opioid related itching or respiratory depression.
- The following data will be collected
 - Quality of recovery (QoR) survey will be filled on post-operative day at 24 and 48 hours.
 - Patients will be evaluated immediately post-operatively in PACU, and 6, 12 and 24 hours post-surgery to determine VAS pain scores at rest and movement on the scale of 0-10. Also highest pain score during first 24 hours will be recorded.
 - Twenty-four hour opioid consumption will be calculated with respect to 24 hours oxycodone use and 24 hours hydromorphone use.
 - Data for postoperative use of ondansetron and naloxone will be collected. Also any postoperative episodes of nausea, vomiting, and itching will also be recorded.

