 - Patient will be followed up until nerve block resolves.
 - Patients' participation in physical therapy will be recorded from physical therapy notes. Specifically, independence in mobility and transfers (independently, with minimal supervision, with moderate supervision, with maximal supervision) and ambulation distance will be recorded using standard PT protocols used at UAB Highlands.
 - The patients will be surveyed regarding their satisfaction with postoperative analgesia. Likert scale will be used to assess their satisfaction level. There will be 4 options to report: very unsatisfied, unsatisfied, satisfied, and very satisfied.
 - The hours from block placement until hospital discharge will be calculated.
- A blinded research associate will evaluate the patients postoperatively to collect data.

Procedure	Length of Time Required of Participants	Frequency of Repetition
Presurgical Evaluation on the day of surgery	30 minutes	once
Randomization on day of surgery	5 minutes	Once
Placement of block	Approximately 30 min.	Once
Post Anesthesia Care Unit (PACU) assessment	10 minutes	Once
First postoperative assessment survey (approximately 24 hours after surgery)	20 minutes	Once

Second postoperative assessment survey (approximately 48 hours after surgery)	10 minutes	Once
--	-------------------	-------------

- Measured Outcomes:

- Primary outcome:
 - Quality of Recovery after surgery assessed on postoperative day 1 (at 24 hours).
QoR-15 scale (form attached) will be used to assess post-operative recovery based on 15 questions: scores will range from 0-150, 0 being the worst recovery and 150 being the best (excellent) recovery.
- Secondary outcomes:
 - QoR-15 at 48 hours
 - VAS scores (0-10) at immediate postoperatively, 6, 12 and 24 hours at rest and movement. VAS score 0 indicates “no pain” and 10 indicates “worst pain experienced”. Highest pain score in first 24 hours will be recorded.
 - Opioid consumption intraoperatively, as well as at 24 hours postoperatively. Oxycodone PO and Hydromorphone iv usage in first 24 hours postoperatively.
 - Incidence of nausea, vomiting and itching in first 24 hours postoperatively.
 - Physical therapist assessment of independence in mobility and transfers (independent, with minimal supervision, with moderate supervision, with maximal supervision)

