Appendix:

QOR-15 FORM

QoR-15 Patient Survey

Date: ___/___/___ Study #: _____

Preoperative Postoperative

PART A

How have you been feeling in the last 24 hours?

(0 to 10, where: 0 = none of the time [poor] and 10 = all of the time [excellent])

1. Able to breathe easily None of the time 0 1 2 3 4 5 6 7 8 9 10 All of the time

2. Been able to enjoy food None of the time 0 1 2 3 4 5 6 7 8 9 10 All of the time

3. Feeling rested None of the time 0 1 2 3 4 5 6 7 8 9 10 All of the time

4. Have had a good sleep None of the time 0 1 2 3 4 5 6 7 8 9 10 All of the time

5. Able to look after personal toilet and hygiene unaided None of the time 0 1 2 3 4 5 6 7 8 9 10 All of the time

6. Able to communicate with family or friends None of the time 0 1 2 3 4 5 6 7 8 9 10 All of the time

7. Getting support from hospital doctors and nurses None of the time 0 1 2 3 4 5 6 7 8 9 10 All of the time

8. Able to return to work or usual home activities None of the time 0 1 2 3 4 5 6 7 8 9 10 All of the time

9. Feeling comfortable and in control None of the time 0 1 2 3 4 5 6 7 8 9 10 All of the time

10. Having a feeling of general well-being None of the time 0 1 2 3 4 5 6 7 8 9 10 All of the time

PART B

Have you had any of the following in the last 24 hours?

(10 to 0, where: 10 = none of the time [excellent] and 0 = all of the time [poor])

11. Moderate pain None of the time 10 9 8 7 6 5 4 3 2 1 0 All of the time

12. Severe pain None of the time 10 9 8 7 6 5 4 3 2 1 0 All of the time

13. Nausea or vomiting None of the time 10 9 8 7 6 5 4 3 2 1 0 All of the time

14. Feeling worried or anxious None of the time 10 9 8 7 6 5 4 3 2 1 0 All of the time

15. Feeling sad or depressed None of the time 10 9 8 7 6 5 4 3 2 1 0 All of the time

Fig. 2. The quality of recovery score (QoR)-15 questionnaire.

Statistical analysis

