Data were summarised using means and standard errors (SE) for continuous outcomes or counts and percentages for categorical outcomes. Two-sample t-tests and chi-square tests were used to compare the two groups. Normality for continuous outcomes was assessed using probability plots and the Shapiro-Wilk test for normality. For any outcomes where normality could not be reasonably assumed, medians and interquartile ranges were reported instead of medians and standard errors, respectively, and the Wilcoxon rank sum test was used in place of the t-test. A 95% confidence interval for differences in means (for continuous outcomes) or relative risks (for categorical outcomes) were calculated. For any non-normally distributed continuous outcomes, asymptotic Hodges-Lehmann confidence limits were calculated.¹⁶ A p-value < 0.05 was considered statistically significant. SAS version 9.4 (SAS Institute Inc., Cary, NC) was used to conduct all statistical analyses.

Sample size calculation

A difference of 8 points is widely accepted as a minimal clinically important difference (MCID) for QoR-15 scores for perioperative interventions.¹⁷ A previous study showed a median QoR-15 score of 115 in the control group for the THA population.¹⁸ Assuming an increase to 123 in the QoR-15 score would be clinically relevant and a standard deviation of 15 points, we estimated that fifty-six patients were needed in each group for 80% power at a 5% significance level.

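### Optional precision gain, not an error: a pre-operative QoR-15 used as a covariate would sharpen the 24-hour primary comparison, but only if adopted before the first patient is randomised

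*Combined protocol and SAP*

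**What the plan says.** - **Endpoint and schedule.** Section 6.0 names QoR-15 (0 to 150) at 24 hours as the primary outcome and QoR-15 at 48 hours as a secondary outcome. The data-collection list says "Quality of recovery (QoR) survey will be filled on post-operative day at 24 and 48 hours". The list of variables contains no pre-operative QoR-15.
- **Analysis.** For normally distributed data, Section 9.0 states that a Student's "t-test will be used to compare the groups. For data that are not normally distributed, a Mann-Whitney tests will be used for comparisons". The closing Statistical analysis section, after the appended form, agrees: "Two-sample t-tests and chi-square tests were used to compare the two groups", with a rank sum test where normality fails. Neither names a covariate for the primary comparison.
- **Sample size.** Both sections give 56 per group for a difference of 8 points, SD 15, 5% significance level and 80% power.
- **Opportunity to collect a baseline.** The Section 6.0 procedure table has a 30-minute row, "Presurgical Evaluation on the day of surgery", listed above "Randomization on day of surgery". Section 2.0 says: "Mean time to complete the 15-question survey is 3 minutes". The appended form is headed "Preoperative Postoperative".
- **Timing.** The projected timeline puts enrolment at 01 2021, data entry and analysis at 04 2021 and write-up at 05 2021. The closing Statistical analysis section is written in the past tense.

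**The concern.** When an outcome can also be measured before randomisation, adjusting for that measurement usually narrows the confidence interval at the same sample size. Here the instrument is short, there is a patient contact before surgery, and the trial is sized at almost exactly 80% power with no stated allowance for loss. The stake is precision only: how tightly the trial can estimate an effect around its 8-point target. Randomisation already protects the unadjusted comparison from bias, so the validity of the primary result is not in question.

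**Working it through.** **Inputs from the documents:** difference 8, SD 15, 56 per arm, 1:1 allocation, 5% level (Sections 5.0 and 9.0). Sidedness is not stated. The stated n matches a two-sided test, since a one-sided test would need 44 per arm.

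**Assumed:** r, the correlation between pre-operative and 24-hour QoR-15. A range from 0 to 0.5 is shown.

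**Step 1. Reproduce the plan's figure.** n = 2 × (1.960 + 0.842)² × 15² / 8² = 55.2, so 56 per arm. This matches.

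**Step 2. Unadjusted comparison at 56 per arm.** SE = 15 × √(2/56) = 2.835 on 110 df. Noncentral t power is 79.9% (80.6% by normal approximation). The 95% CI half-width is 1.982 × 2.835 = 5.62 points.

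**Step 3. ANCOVA at 56 per arm.** SE = 15 × √[(2/56) × (1 − r²) × (1 + 1/(2×56 − 4))] on 109 df. The last factor is the price of estimating the covariate slope. Completers are per arm for 80% power.

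| r (assumed) | SE | Power | CI half-width | Completers |
|---|---|---|---|---|
| Unadjusted | 2.835 | 79.9% | 5.62 | 57 |
| 0 | 2.848 | 79.5% | 5.64 | 57 |
| 0.1 | 2.834 | 79.9% | 5.62 | 57 |
| 0.2 | 2.790 | 81.1% | 5.53 | 55 |
| 0.3 | 2.717 | 83.1% | 5.38 | 52 |
| 0.4 | 2.610 | 85.9% | 5.17 | 48 |
| 0.5 | 2.466 | 89.5% | 4.89 | 43 |

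The unadjusted 57 differs from the plan's 56 only because it uses the noncentral t. ANCOVA and the unadjusted test have equal power at r = 0.097.

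**Step 4. Missing baselines.** If a share m of baselines is missing and replaced by the overall mean, r becomes r × √(1 − m). With an assumed m of 0.10, power at r = 0.2 / 0.3 / 0.4 / 0.5 is about 80.9 / 82.8 / 85.3 / 88.5%.

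**Step 5. Why not a change score.** With equal SDs, the SD of change is 15 × √[2(1 − r)]. That is 17.7 at r = 0.3 and 16.4 at r = 0.4, giving power of 66.5% and 73.1% (normal approximation) against 80.6% unadjusted. Below r = 0.5 a change-score analysis would be worse than the current plan.

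**The case against.** The case for leaving the plan alone is strong, and most of it stands.

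- **Nothing is wrong or inconsistent.** The sample size was computed for an unadjusted comparison, and no section promises a baseline score. A reader might infer that the primary analysis is invalid or underpowered without adjustment. The documents do not support that: 56 per arm reproduces, and 79.9% against 80.6% is only the difference between noncentral t and normal formulas.
- **It can probably no longer be done.** A baseline cannot be collected after surgery, and both the timeline and the past tense point to finished data collection. The documents do not state enrolment status, so this is likely rather than certain. A reader might also infer that the change could be made at any time while enrolment is open. It could not serve as the primary analysis then, because patients already enrolled would have no baseline.
- **The benefit rests on an unknown.** At r = 0.3 the half-width shrinks by only 5.62 − 5.38 = 0.24 points. The form gives some reason to expect a modest r: it asks about the last 24 hours, and an item such as "Getting support from hospital doctors and nurses" may mean little on the morning of surgery.
- **The form's header is weak evidence.** It belongs to a standard questionnaire reproduced with its figure caption. A reader might infer that a baseline was planned and then forgotten, or collected and not used. The header shows only that pre-operative use is feasible. Likewise, the order of rows in the procedure table suggests, but does not state, that the evaluation precedes randomisation, and nothing says that its 30 minutes include spare time.

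What remains is the asymmetry: at worst about 0.4 percentage points of power are lost, while a moderate correlation gains several.

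**Conclusion.** This is a low-priority, optional improvement. Relative to 79.9% unadjusted, baseline ANCOVA changes power by −0.4 percentage points at r = 0, +1.2 at 0.2, +3.2 at 0.3, +6.0 at 0.4 and +9.6 at 0.5. The gain is small at r of 0.2 to 0.3 and clear from about 0.4. These figures assume the plan's SD of 15, 56 analysed patients per arm, a linear baseline relation and a two-sided 5% test. The size of r is an assumption throughout. The improvement applies only if adopted before the first patient is randomised, and the documents suggest that point has probably passed.

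**What to change.** Confirm enrolment status first.

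**If no patient has been randomised:**

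1. Collect QoR-15 at the presurgical evaluation, before the allocation envelope is opened and before any sedation.
2. Prespecify, as the primary analysis, ANCOVA of 24-hour QoR-15 on arm and baseline QoR-15, reporting the adjusted difference with its 95% CI. Do not use a change score.
3. Keep every patient with a 24-hour score, replacing a missing baseline by the overall baseline mean.
4. Report the planned t-test or rank test as a sensitivity analysis.

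**If patients were enrolled without a baseline, or data collection is complete:** keep the planned unadjusted test as primary and label any covariate adjustment post hoc.

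**Cost:** about 3 minutes per patient, some missing baselines, and about 0.4 percentage points of power if r is 0. The paperwork is more than a SAP edit: the data-collection schedule, the participant time table and the variable list in Section 6.0 also need amending.

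### The primary 24-hour QoR-15 comparison is valid but uses none of the baseline variables the trial already collects, so it may give up some precision that a short pre-specified adjustment could recover

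*Combined protocol and SAP*

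**What the plan says.** The primary outcome in section 6.0 is the QoR-15 total (0 to 150) at 24 hours.

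Section 9.0 sets the comparison by distribution. For normal data, Student's "t-test will be used to compare the groups"; for non-normal data, "a Mann-Whitney tests will be used for comparisons". The Statistical analysis section appended after the QoR-15 form takes the same approach: "Two-sample t-tests and chi-square tests were used to compare the two groups", with the Wilcoxon rank sum test as the fallback. Neither section names a covariate-adjusted model for the primary outcome.

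The data list in section 6.0 includes age, gender, BMI, "Surgical approach" and "ASA physical status". Section 9.0 describes demographic variables but brings none of these five into a comparison. The only multi-factor analysis is for anaesthetic type: "The planned sub-group analysis will be conducted for GA vs. Spinal using a 2x2 ANOVA test".

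Section 5.0 describes 1:1 randomisation in permuted blocks of variable size and states no stratification factor. Section 9.0 sizes the trial at 56 per group for a "Minimal Clinically Important Difference (MCID) of 8 points for QoR-15 score", with SD 15, 5% significance and 80% power.

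**The concern.** Neither the design nor the analysis uses prognostic information. Eligibility is wide (any adult, ASA I to III, no restriction on approach), so some of the listed variables may well predict recovery at 24 hours. If they do, an unadjusted test leaves explainable variation in the error term. The planned power has no slack: it is almost exactly 80%, and no dropout allowance is stated.

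There is also a pre-specification gap. With five such variables collected and no rule for using them, any adjusted analysis that appears later could have been chosen after seeing which variable looked unbalanced. Naming the covariates in advance closes that route.

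**Working it through.** **Inputs.** Difference 8, SD 15, 56 per arm (N = 112), 5% significance and 80% power, all from section 9.0. Sidedness is not stated; two-sided reproduces the plan's figure, whereas one-sided gives 44 per group. The documents give no R² between any covariate and QoR-15, so R² is assumed over 0 to 20%.

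**1. The plan's own figure.** n per arm = 2 × [15 × (1.960 + 0.842) / 8]² = 55.19, rounded up to 56. This reproduces. The standard error of the unadjusted difference is 15 × √(2/56) = 2.83 points. Power at 56 per arm is 80.6% by the normal approximation and 79.9% by the noncentral t. The 95% CI half-width is 5.62 points.

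**2. Adjusted analysis, net of its cost.** With p covariate terms:
- residual SD = 15 × √(1 − R²);
- residual degrees of freedom = 110 − p;
- variance inflation from estimating the covariate effects ≈ 1 + p/(N − p − 3);
- SE = residual SD × √(2/56 × inflation).

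For p = 3 (for example age, sex, and ASA III versus I–II), inflation = 1 + 3/106 = 1.028. For p = 6 (age, sex, BMI, two ASA terms, and one approach term, which assumes two approaches), inflation = 1 + 6/103 = 1.058.

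| Assumed R² | SE, 3 terms | Power, 3 terms | SE, 6 terms | Power, 6 terms |
|---|---|---|---|---|
| 0 | 2.88 | 78.8% | 2.92 | 77.6% |
| 5% | 2.80 | 80.8% | 2.84 | 79.6% |
| 10% | 2.73 | 82.8% | 2.77 | 81.7% |
| 20% | 2.57 | 86.9% | 2.61 | 86.0% |
| Unadjusted | 2.83 | 79.9% | 2.83 | 79.9% |

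A simulation of the six-term model (8,000 repetitions per scenario) gave 78.1%, 80.5%, 81.3% and 85.9%, in line with the last column.

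**3. Break-even.** The SE falls only if (1 − R²) × inflation < 1, that is, R² > 1 − 1/inflation. This is 2.8% for three terms and 5.5% for six.

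**4. What chance imbalance contributes.** Assume a factor present in half the patients that shifts QoR-15 by 6 points. The SD of the between-arm difference in its proportion is √(2 × 0.25/56) = 0.094, so the 95% range is ±1.96 × 0.094 = ±18.5 percentage points, or ±1.1 QoR-15 points. Its share of the variance of the estimate is (6 × 0.0945)² / 2.83² = 0.32/8.04 = 4%. That equals the factor's own R², 36 × 0.25/225 = 4%. The imbalance is therefore already inside the 2.83-point SE and is not an extra error on top of it. If 4% were all that the covariates explained, the three-term model would have 80.4% power and the six-term model 79.2%, against 79.9% unadjusted.

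**The case against.** The strongest reply is that nothing here is wrong. Under 1:1 randomisation the unadjusted difference is unbiased, the sample size matches the planned test, and an unadjusted primary analysis is legitimate. No figure in the documents shows that these variables reach break-even. All of this stands, and it limits the point to an optional gain in efficiency and clarity.

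Three stronger readings are tempting, and the documents do not support them.

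- *The plan gives away free precision.* Adjustment has a cost at N = 112. If the covariates explain nothing, power falls by about 1 point with three terms and about 2 with six.
- *Chance imbalance biases the primary estimate because randomisation is not stratified.* It does not. Imbalance is random variation already counted in the SE. Adjustment corrects the estimate for observed imbalance; it does not remove a bias.
- *Surgical approach must be a covariate because the block targets the anterior capsule.* That rationale points, if anywhere, to a block effect that differs by approach, which a main-effect term does not address. The mix of approaches at this single hospital is not given. Section 6.0 does not say when approach is recorded or whether it is fixed before randomisation, which takes place on the day of surgery.

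Timing is a further fair objection. The appended Statistical analysis section is in the past tense and may describe a completed analysis. If so, replacing the primary model now would itself be a post hoc change.

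**Conclusion.** The point holds as a low-cost improvement. The primary comparison is valid, and 56 per arm is right for it, but it ignores baseline variables already on the collection list and may give up some precision.

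The size depends on an assumed R². With three covariate terms, the change in power against 79.9% runs from a loss of about 1 point (R² = 0) to gains of about 3 points (R² = 10%) and 7 points (R² = 20%). A six-term model does worse at every R² in the table and falls slightly short of the unadjusted test at R² = 5%, so a short list is preferable unless the extra variables add real explanatory power. The figures rest on SD 15, 56 analysed per arm, a two-sided 5% test and an approximate inflation factor. The gain in pre-specification does not depend on R².

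**What to change.** In section 9.0 and the appended Statistical analysis section, before unblinding:

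1. Define the primary analysis as a linear model of 24-hour QoR-15 on arm plus a short, named list of covariates fixed before randomisation, for example age, sex and ASA class as a single III versus I–II term.
2. Report the adjusted mean difference with a 95% CI, on the same scale as the 8-point MCID.
3. Keep the planned unadjusted test as a sensitivity analysis.
4. Add surgical approach only if it is confirmed to be fixed before randomisation.
5. If the data are already unblinded, leave the unadjusted test as primary and report the adjusted model as a labelled supportive analysis.

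The cost is wording in two sections and three residual degrees of freedom out of 110, with a worst-case loss of about 1 power point. No new measurement, visit or patient is needed.
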